the same hydration metrics - blood pressure (BP), weight, and ultrafiltrate volumes - using home monitoring equipment (BP cuff, body weight scale, and hanging scale). The no-app group will manually enter the information into their “PD logbook”- the handwritten paper booklet which is usual care. In contrast, the app group will automatically collect and enter the same information into the CKD-PD app using NFC technology on their smart phone. It will be displayed in the CKD-PD app for the patient and uploaded to the CKDNET database in the Thai Care Cloud; it then can be viewed on the CKD-PD web application by the PD clinic staff. Patients will monitor their hydration status on a graphical display on their smartphone. PD clinic staff will be notified daily about “action required” alerts on the web application. For example, systolic BP greater than 140 mmHg, diastolic BP greater than 90 mmHg, weight gain greater than 3% based on dry weight, or ultrafiltrate volume < 500 milliliters will trigger a response from the PD clinic. Nephrologists will make clinical interventions to treat OH according to standard practice in Thailand, which include BP and diuretic medication adjustments, change in diet or fluid intake, dialysis prescription adjustments or referral for urgent clinical evaluation. Clinical interventions can occur at unscheduled patient contact (e.g. patient call) or scheduled patient contact (routine clinic visit) Our primary outcome measure will be the incidence of clinical interventions for OH, both routine and urgent, in 1 year from enrollment. Secondary outcome measures include OH related complications, hospitalizations and deaths, and will be collected from PD clinic and hospital records, and the CKDNET database.

Setting and study population: The study will be conducted at the PD clinics at Srinagarind Hospital (N=100) the academic referral hospital affiliated with Khon Kaen University, Khon Kaen Hospital (N=50) the government referral hospital for Khon Kaen province, and Chaiyaphum Hospital (N=50), the government referral hospital for the neighboring Chaiyaphum province in northeast Thailand. We will recruit 200 patients with end-stage renal disease on PD from KKH to achieve a total sample size of 160.

Inclusion criteria are

- patients with CKD from any cause on home based peritoneal dialysis
- age ≥ 18
- access to a smartphone capable of running the CKD-PD app
- ability of the patient or surrogate to demonstrate successful use of the CKD-PD app

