addition to training on how to use other features on the CKD-PD app including self-monitoring of hydration metrics and in-app communication with PD staff. The no-app group will receive instructions on how to record the same information in their paper PD log book as well as information about how to contact the clinic by phone. Research staff will also make a home visit for app-group participants at the start of data collection to confirm correct equipment set up and use.

Clinical interventions: In both the app and no-app groups, clinical interventions for OH can occur at either an unscheduled patient contact (e.g. phone call, clinic visit, or emergency visit) or at a scheduled clinic visit. In the app group, clinical interventions can also occur when an action required notification occurs, and the PD clinic staff contacts the patients and determines that a change in treatment is indicated to manage the OH. This occurs when a patient is flagged as an outlier (action required) because one or more of the hydration metrics is outside of the established acceptable range (see paragraph directly below). The PD clinic staff, after reviewing the patient's hydration metrics, will initiate contact with the patient, to review hydration metrics and patient symptoms. If the PD nurse confirms abnormal hydration metrics (action required) or clinical symptoms consistent with OH, the case will then be referred to the nephrologist to review the information and determine the need for a clinical intervention. Nephrologists will make clinical interventions according to standard practice in Thailand, summarized as guidelines and provided to nephrologists and PD clinic staff for reference at the beginning of the study. An episode of clinical intervention is defined as treatment intervention for abnormal hydration metrics or clinical symptoms of OH with 1 or more changes in patient management: change in medications, dialysis prescription, fluid or salt restriction, or urgent clinic/hospital visit. A contact that results in no change in management is not considered a clinical intervention for OH.

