Monitoring CKD-PD smartphone and web applications: We will set 3 categories to be used by PD clinic staff when monitoring hydration metrics on the CKD - PD web application: normal, monitor, and action required. Based on criteria specified by KKU nephrologists, deviations in weight of >3% from baseline dry weight, BP>140/90, and ultrafiltration volume of <500 ml will be used as baseline parameters for triggering an outlier alert for action required, indicating that the patient's hydration metrics need to be reviewed. We will also set critical values for hydration metrics, which require patient to go directly to the emergency department. We expect that some patients will require different parameters for triggering an outlier alert. In order to address this issue, a study nephrologist will provide normal and action required values for weight, blood pressure, and ultrafiltration volumes for each patient, at the time of enrollment after reviewing previous values from their PD logbook. During the study, the patient's nephrologist will have the option to modify the notification parameters. Hydration metric values between normal and action required will be categorized as monitor status.

PD clinic staff nurses will receive a list of patients with action required alerts once a day. They will review the hydration metrics and contact the patient(s), ask about symptoms, and have the nephrologist review the data and case to determine need for clinical intervention.

PD patients will also have the ability to self-monitor using the visual display of hydration metrics on the CKD-PD app. Planned features to simplify patients understanding of their fluid status include color coded zones corresponding to the normal (green), monitor (yellow), and action required (red) categories. During training, patients will be instructed to contact the PD clinic if one or more of the hydration metrics indicate action required.

Planned research procedures: Our project has 5 research procedures, all of which will collect private, identifiable patient information.

1. *Monitoring for abnormal hydration metrics by PD clinic staff:* PD clinic staff will review the CKD-PD web application daily for outlier alerts. Outliers are determined based on the hydration metric parameters set by the nephrologist at enrollment. See 4.2.a.3 below.

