2. *Clinical intervention for overhydration:* Change in medical treatment in response to OH detected by clinical symptoms or hydration metrics. Interventions may include a change in medications to treat OH such as anti-hypertensives or diuretics, dialysis prescription, dietary sodium/fluid restriction, referral for evaluation in clinic, or hospitalization. This information will be collected in the electronic PD clinic study log at the time of the clinical intervention.
3. *Unscheduled clinic contacts:* When patients in either group make an unscheduled contact with the PD clinic this will be recorded in the PD clinic electronic study log. Unscheduled clinic contact can also occur in the “app” group when PD clinic staff contact a patient in response to abnormal hydration metrics. Unscheduled contacts include any phone call, text, social media, or web app message, and unscheduled visit to the PD clinic or emergency department. The information collected included patient name/MR#, reason for contact, mode of contact, who initiated contact, date and time of day, and action taken. Unscheduled clinical interventions will be recorded at the time of the event.
4. *Scheduled clinic contacts:* Patients in both groups will have regularly scheduled clinic visits, typically bimonthly. Clinical interventions for OH made during this visit will be recorded in the electronic PD clinic study log. A medical record review will also occur at each visit to collect any other hospitalizations, complications, or clinical interventions that may have occurred in the interim.
5. *CKDNET database review:* In order to ensure all events have been captured, we will review the CKDNET database, which has all inpatient and outpatient visits, on a bimonthly basis.

Data collection overview

Data elements for analysis of covariates at enrollment: These will include: age, sex, educational level, cause of CKD, eGFR, co-morbidities (e.g. diabetes, hypertension, albumin level), previous hospitalizations for OH, smoking status, distance from clinic, months on PD, months of CKD-PD usage, and app user type (patient or surrogate). The source will be medical records and patient interview at time of enrollment.

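### The weight trigger and the primary event are each worded in two ways, so management changes made for values that are not overhydration could be counted, with detection favouring the app arm

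*Combined protocol and SAP*

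**What the plan says.** *Weight trigger.* The Aim 2 Overview, in an illustrative list of alert values, has "weight gain greater than 3% based on dry weight". The paragraph on monitoring the smartphone and web applications lists among its baseline parameters "deviations in weight of >3% from baseline dry weight". It adds that "a study nephrologist will provide normal and action required values for weight, blood pressure, and ultrafiltration volumes for each patient" at enrolment, and the patient's own nephrologist may alter the limits later.

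*Primary event.* The Clinical interventions paragraph gives the formal definition: "An episode of clinical intervention is defined as treatment intervention for abnormal hydration metrics or clinical symptoms of OH", with at least one listed change in management. Contacts that change nothing are excluded. Item 2 of the Aim 2 Planned research procedures describes the event as "Change in medical treatment in response to OH detected by clinical symptoms or hydration metrics".

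*Alert route, app arm only.* The Clinical interventions paragraph introduces this route as one in which the clinic contacts the patient and "determines that a change in treatment is indicated to manage the OH". Further on it sets the condition for referral: "If the PD nurse confirms abnormal hydration metrics (action required) or clinical symptoms consistent with OH". The nephrologist then decides whether an intervention is needed.

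*Recording.* Under Data collection overview, the study log holds the type of intervention, the symptom or metric abnormality behind it, and whether the contact was scheduled. No field is described that states whether the reason was overhydration (OH).

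**The concern.** The primary outcome is a count of interventions for OH, and the hypothesis is that the app raises it. A count of that kind is only interpretable if every counted event is treatment of OH. An undirected weight trigger brings low weights to the clinic's attention. A definition that can be met by treatment for an abnormal metric may then count the response. A change made because a patient is below dry weight is not treatment of OH and may be its opposite. Because the alert system that surfaces such values runs in one arm only, the error would not be expected to cancel between arms. It would tend to enlarge the estimated rate difference in favour of the app.

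**Working it through.** **Step 1: follow one case through the text.** Take a management change made because weight is more than 3% below dry weight.

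| Text | Does the case pass? |
|---|---|
| Aim 2 Overview, example trigger (gain) | No |
| Monitoring paragraph, baseline trigger (deviation) | Yes, unless that patient's own limits exclude it |
| Clinical interventions, introduction of the alert route | No: the change must be to manage OH |
| Clinical interventions, condition for referral | Yes: a confirmed abnormal metric is enough |
| Clinical interventions, formal definition | Yes if *of OH* attaches to symptoms only; no if it governs both terms |
| Planned research procedures, item 2 | No: the change must respond to OH |

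The answer depends on which sentence is applied, and the plan does not say which governs.

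**Step 2: compare the arms.** The definition applies to both arms. Both record the same metrics, and interventions at scheduled visits count in both. Only the app arm has daily alerts, staff-initiated contact in response to them, and colour-coded prompts to call the clinic. The opportunity to detect and act on an out-of-range value between visits is therefore greater in the app arm.

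**Step 3: reproduce the plan's figures** (Statistical Design and Power). Control rate: 4 × 52 / 91 = 2.29, stated as 2.3 per patient-year. App rate: 4.6. Precision of 25% of the difference: 0.25 × 2.3 = 0.575. Then n = 1.96² × (2.3 + 4.6) / 0.575² = 80.17, which matches the stated 80 per group. The point made here changes no sample size.

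**Step 4: sensitivity, by assumption only.** Suppose the app has no true effect on treatment of OH, both arms run at 2.3 per patient-year for one year, there are 80 patients per group, and r extra non-OH changes per patient-year are counted in the app arm and none in control. With variance φ times Poisson, allowed for in the test:

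z = r / √(φ(2.3 + 2.3 + r)/80), and the chance of significance in favour of the app is Φ(z − 1.96).

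For r = 0.5 and φ = 1: z = 0.5 / √(5.1/80) = 1.98, so Φ(0.02) = 0.51.

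| r per patient-year | r / 2.3 | z (φ = 1) | Chance, φ = 1 | φ = 2 | φ = 4 |
|---|---|---|---|---|---|
| 0.25 | 11% | 1.02 | 17% | 11% | 7% |
| 0.5 | 22% | 1.98 | 51% | 29% | 17% |
| 1.0 | 43% | 3.78 | 97% | 76% | 47% |

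An even chance of significance needs r of about 0.50, 0.71 or 1.04 for φ = 1, 2 or 4. The values of r and φ have no source in the documents. If such events were also counted in control, only the excess in the app arm would contribute to the difference.

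**The case against.** The case for reading the plan as already sound is substantial.

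- The outcome is called intervention for OH in the Overview, the analysis paragraph, the research procedures and the outcome measures. The alert route is introduced with an OH indication. A reader might infer that the plan counts any treatment for an abnormal metric, or that no OH judgement is asked for anywhere. The documents support neither.
- In the formal definition, *of OH* can govern both terms. Read so, it agrees with item 2 of the research procedures.
- The gain trigger is only an example, and the deviation trigger is a baseline that can be set for each patient. An alert is not an event: nurse confirmation, nephrologist review and a change in management must all follow.
- A reader might infer that miscounted events would fall almost wholly in the app arm. The documents give no split, and logbook review at clinic visits could produce such events in control too.

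All of this narrows the point. What stands against it is that the formal definition itself does not state an OH requirement for the metrics route, referral can rest on an abnormal metric alone, and no adjudication of the reason for an event is described. Individual limits need not run in one direction. The plan itself gives a low blood pressure (below 80/40) as an example of a critical hydration value, so low values are within what it treats as abnormal. The primary endpoint should not depend on how one phrase is parsed.

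**Conclusion.** The concern holds as an ambiguity that leaves room for bias, not as a bias the plan prescribes. Two statements of the weight trigger differ in direction, and two statements of the primary event differ in whether OH must be the reason. Under the literal reading of the formal definition, a change made for weight below dry weight can be counted. Unequal detection means any such counting would tend to favour the app.

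The size is unknown. It would be wrong to take 17%, 51% or 97% as an estimate of this trial's false-positive risk: those figures rest on assumed event rates, no true effect, no such events in control and pure Poisson variance, and they fall with overdispersion. They show only that, under those assumptions, about one miscounted change per app patient every two years would be enough for a roughly even chance of a significant result. The point should be settled before events are classified.

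**What to change.** 1. Reconcile the weight trigger between the Aim 2 Overview and the monitoring paragraph. Which one applies is for the nephrology team to decide.
2. Reconcile the formal definition under Clinical interventions with item 2 of the Planned research procedures, so that in both arms an event enters the primary outcome only if its recorded reason is OH.
3. Tabulate management changes made for other out-of-range values separately, by arm. They remain visible without entering the primary count.

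The cost is protocol wording and possibly one added log field stating whether the reason was OH, because the log already captures the symptom or metric abnormality but not that explicit judgement. Assessing the logged reason without knowledge of arm would be a useful addition where feasible. Sample size and the choice of clinical thresholds are unaffected.

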
Exclusion criteria are

- vulnerable populations
- unwillingness to sign consent or participate in the study.

Recruitment plan: The study population will be recruited from patients at the nephrology clinic at each of the participating hospitals who are undergoing peritoneal dialysis. Participants will be recruited over a 3-month period

at scheduled PD clinic appointments. This is feasible since all patients are seen within a 2-month interval. Accrual will be monitored by Thai study staff by recording enrolled participants in the electronic study log and a list of patients from KKH who declined enrollment or were excluded. Participants will be informed about the possibility of participating in a research study using a smartphone app to help collect information about the peritoneal dialysis, which they currently collect using a handwritten log book. They will be provided with written and verbal information about the research. All questions will be answered. Participation is completely voluntary, and participants can withdraw from the study at will.

Retention plan: Retention will be maximized by frequent involvement and contact with the research team and PD clinic staff. Patients undergoing peritoneal dialysis already require frequent clinic contact and they have a long-standing relationship with the MDs and RNs in the nephrology clinic. Compliance with PD clinic appointments is estimated at over 90%; participants who miss their scheduled appointments will be contacted by PD clinic and rescheduled.

Planned distribution of subjects by sex/gender, race, and ethnicity: We will not select or reject patients based on gender, race or ethnicity. The racial and ethnic composition of the general population, the PD patient population, and the research study population is nearly exclusively Thai. The study will take in place at Khon Kaen province, located in an area of nearly exclusively Thai ethnicity. We expect nearly equal numbers of male and female enrollment given the nearly equal rates of PD between the sexes. We base this assumption on the reported prevalence of females on PD (50.8%) and males (49.2%) [8].

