Baseline variables of the CKD-PD app and no-app groups will be described by summary statistics. Percent distribution will be presented for all categorical variables. Mean with its standard deviation and median (Minimum: Maximum) will be presented for continuous variables. The primary outcome will be assessed by comparing the difference between the CKD-PD app group (intervention) and the no-app group (control), in incident rate (or Poisson count) of intervention for OH. A linear mixed model with an identity link and a Poisson distribution will be performed. By this modeling, the incidence rate difference and its 95% confidence interval will be estimated to answer the primary research question. Estimations will be adjusted for effects of important covariates that are imbalanced at baseline. Effect size will be calculated for secondary outcomes. All analyses will be performed using STATA version 14 (StataCorp, College Station, TX), using a significance level of 0.05. All statistical tests will be two-sided.

Randomization

Participants (Srinagarind N=100, Khon Kaen N=50, Chaiyaphum N=50) will be randomized into two equal groups at each site, one using the CKD-PD app (app group, N=50/25/25), and one receiving usual management (no-app group, N=50/25/25), using 4-block computer randomization in STATA. They will be assigned a PD clinic visit day based on their randomization allocation to reduce contamination or cross talk between the 2 study groups.

Delivery of intervention

Definition of study intervention:

Our study intervention is defined as the CKD-PD app, home hydration metric measurement equipment, and the monitoring of the uploaded hydration metrics to the CKDNET database.

Collection of hydration metrics: After enrollment, participants in both groups will undergo training on how to collect daily hydration metrics: body weight, blood pressure, and dialysate inflow and outflow volumes for each cycle. The app group will receive training on how to enter hydration metrics using NFC on the CKD-PD app, in

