Clinical interventions used: We will record the type of clinical intervention, patient symptom/hydration metric abnormality, whether it was occurred from a scheduled or unscheduled communication, and ordering clinician. This information will be recorded in an electronic study log at time of PD clinic visit, or time of communication to patients.

Outcome measures: Our primary outcome measure will be the incidence of clinical interventions for OH in 1 year from enrollment. Secondary outcome measures include OH-related complications

Drop out/Lost to follow up: The number of patients who drop out, are lost to follow up or died during the study period will be collected. This information will be collected from chart reviews and PD clinic communications and recorded in the electronic clinic study log.

PD clinic/patient communications: We will also collect data about communications between PD clinic staff patients or their surrogates by logging phone calls and messaging app contacts. This information will include who initiated the call, whether or not it resulted in a clinical intervention, the type of clinical issue, and mode of communication. This information will be recorded in the PD clinic electronic study.

Potential risks to participants: This study poses low risk to participants with regard to physical, psychological, social, cultural or legal aspects as both groups receive the same standard of care as currently provided to PD patients at the study site nephrology clinics, including routine clinic appointments, medications, dialysis prescriptions, dietary recommendations, educational and other community support networks, and urgent services e.g. phone contact to PD clinic, unscheduled clinic visits, and emergency care. We have identified some potential specific risks including data breaches, lost or malicious hacking of computers, loss of privacy, concern about change or access to PD care, over or under identification of overhydration, failure to detect life threatening outlier data points in a timely fashion, technology failure, communication failures and errors, and unintended consequences of using a new technology. Strategies to mitigate these risks are discussed below. Alternative strategies available to participants are the option to decline or withdraw from the research at any time.

Informed Consent and Assent

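### The plan does not say whether treatment changes at the enrolment visit count toward the one-year outcome, and the hydration values reviewed at enrolment are not planned adjustment covariates

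*Combined protocol and SAP*

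**What the plan says.** All references are to Aim 2 of the combined protocol unless stated otherwise.

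- **Outcome window.** Data collection overview, Outcome measures: "Our primary outcome measure will be the incidence of clinical interventions for OH in 1 year from enrollment". The Overview adds that both kinds of contact count: "incidence of clinical interventions for OH, both routine and urgent, in 1 year from enrollment".
- **Where enrolment happens.** Recruitment plan: "at scheduled PD clinic appointments. This is feasible since all patients are seen within a 2-month interval".
- **What is logged.** Planned research procedures, item 4 (scheduled contacts): "Clinical interventions for OH made during this visit will be recorded in the electronic PD clinic study log". The enrolment visit is not excepted. The Clinical interventions paragraph also accepts scheduled visits as a source of events in both arms.
- **When the app starts.** Collection of hydration metrics: "After enrollment, participants in both groups will undergo training on how to collect daily hydration metrics". App-arm patients then have a home visit when data collection begins. The interval from enrolment is not given.
- **Review at enrolment.** Monitoring CKD-PD smartphone and web applications: a study nephrologist sets each patient's weight, blood pressure and ultrafiltration limits "at the time of enrollment after reviewing previous values from their PD logbook".
- **Covariates.** The enrolment data elements include "previous hospitalizations for OH, smoking status, distance from clinic, months on PD", with demographics, co-morbidities, prior app use and user type. They name no blood pressure, weight or ultrafiltration value. Statistical Design and Power adjusts only for important covariates that turn out imbalanced.

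**The concern.** Two gaps meet at the same visit.

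First, the clock has no defined start relative to the enrolment visit. A treatment change made there responds to fluid that built up under usual care. For a new user, the app cannot have caused it. If the plan leaves this open, sites may score the same visit differently. Events common to both arms add variance. If the visit were handled differently by arm, the comparison itself would be affected, and the outcome is a clinician's decision in a trial where the care teams know who uses the app.

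Second, the quantities most directly tied to later OH treatment are already being read from the logbook at enrolment, yet they have no planned role in the analysis. Adjustment triggered by observed imbalance also leaves the final model to be chosen after the data are seen.

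**Working it through.** **Inputs from Statistical Design and Power.** The control rate is 2.3 per patient-year (4 × 52 / 91 = 2.29), based on contacts outside scheduled appointments. The app rate is 4.6, the planned difference 2.3, and the size 80 per group at 25% precision with two-sided 5%. The planned effect measure is the incidence rate difference.

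**Inputs assumed (the documents give no figure).** A treatment change occurs at 20-50% of scheduled visits, equally in both arms. Visits fall at months 0, 2, ..., 12, so there are seven including enrolment. Counts have Poisson variance, as in the plan's own calculation.

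**1. The plan's figure.** n = 1.96² × (2.3 + 4.6) / (0.25 × 2.3)² = 80.17. The stated 80 reproduces as a precision calculation, so there is no arithmetic error on this point.

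**2. Enrolment visit counted equally in both arms.** With an added p events per patient in each arm, the difference is (4.6 + p) − (2.3 + p) = 2.3, unchanged. The variance rises by 2p. The outcome also counts the other six scheduled visits, so they belong in the base at the same p:

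| p | Rates without enrolment visit | Sum of rates, without → with | SE ratio | 95% half-width at 80 per group |
|---|---|---|---|---|
| 0.2 | 2.3 + 1.2 = 3.5; 4.6 + 1.2 = 5.8 | 9.3 → 9.7 | √(9.7/9.3) = 1.021 | 0.668 → 0.682 |
| 0.5 | 2.3 + 3.0 = 5.3; 4.6 + 3.0 = 7.6 | 12.9 → 13.9 | √(13.9/12.9) = 1.038 | 0.787 → 0.817 |

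The SE of the difference therefore rises by about 2-4%. Leaving the other six visits out of the base would give √(7.3/6.9) = 1.029 to √(7.9/6.9) = 1.070. That overstates the effect, because it adds one scheduled visit to a rate that contains none.

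**3. Enrolment review that differs by arm (conditional).** If the review prompted one extra change in 10-30% of app patients only, the false difference would be 0.1-0.3. That is 0.1/2.3 = 4% to 0.3/2.3 = 13% of the planned difference. Neither the premise nor the percentages come from the documents.

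**4. Adjusting for baseline hydration.** If the added covariates correlate ρ with the one-year count, the interval width scales by about √(1 − ρ²). For ρ = 0.3 this is √0.91 = 0.954. For ρ = 0.5 it is √0.75 = 0.866. Intervals are 5-13% narrower. This compares with an unadjusted analysis whose SE reflects real variation between patients. A model that forces the variance to equal the mean would not show the gain in the same way.

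**The case against.** The strongest reply is that the plan never says day-0 changes count. A year measured from enrolment can be read as starting after that visit, and the text places the start of data collection after training. This stands: the defect is an undefined start, not a rule that scores pre-app events.

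A reader might infer a built-in excess in the app arm, because the threshold review is described under app monitoring and only that arm has alerts. The documents do not support this. The limits are to be provided for every patient. The background section on the app describes logbook review at the two-monthly visit as current practice, so controls' logbooks are read too. Randomization is 1:1 within site. What remains open is whether the review comes before allocation.

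A reader might also infer that no baseline is kept, or that nobody is on the app at enrolment. Neither follows. The covariate list is open-ended and includes prior OH hospitalizations, individual limits and a baseline dry weight are needed for alerts, and the study log would identify an enrolment-visit change. Some enrollees may already use the app: 42 current users are mentioned, and months of use is a covariate.

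Finally, counting from randomization is ordinary intention-to-treat practice, and starting the next day still precedes app set-up. That is correct. A set-up lag of 1-8 weeks (assumed) would lower the difference to 2.3 × 51/52 = 2.26 or 2.3 × 44/52 = 1.95, which is toward no effect. The fix below does not remove that lag and need not.

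**Conclusion.** The point holds as a gap in definition and a missed use of available data. The plan should say whether enrolment-visit changes are scored. Scored equally, they leave the planned difference at 2.3 and raise its SE by roughly 2-4%, given a change at 20-50% of scheduled visits. A fall in the rate ratio is not the relevant harm, because the planned estimate is a difference. Bias is possible only if the threshold review differed by arm or followed known allocation, and the documents settle neither.

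The covariate gap is the larger practical matter. Blood pressure, weight relative to dry weight and ultrafiltration are strong candidate predictors, are reviewed at enrolment, and are not planned for use. The 5-13% gain rests entirely on the assumed correlation of 0.3-0.5. This is a cheap improvement and does not by itself threaten the trial's conclusion.

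**What to change.** 1. **Start of the count.** Log the enrolment visit's treatment decisions and complete the logbook and threshold review for every patient before randomization. Start the one-year count the day after randomization in both arms. This removes enrolment-visit events and the route to arm-specific review.
2. **Covariates.** Add enrolment blood pressure, weight relative to dry weight, ultrafiltration, and OH intervention at the enrolment visit (yes/no) to the enrolment data elements. Name them as prespecified covariates in the primary model, in place of selection by observed imbalance.

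The cost is protocol wording, a few fields taken from a logbook already in hand, and a brief review for controls. The model is slightly larger. An identity-link Poisson model can fail to converge when fitted means approach zero, so convergence should be checked and a fallback stated in advance.
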